- b. Are certain test procedures and stimuli particularly sensitive to the deficits found with this population of veterans and are deficit patterns influenced by the coexistence of PTSD?
- c. Does the addition of background noise produce over-additive effects in this population of veterans and does PTSD increase the effect?
- d. Does this population of veterans perceive and demonstrate benefit when fitted with hearing aids that provide mild high-frequency gain and does PTSD influence benefit?
- e. Is hearing aid benefit predictable by measures of auditory processing, speech perception, psychoacoustic, verbal working memory, and language processing? Furthermore, does the coexistence of PTSD influence the relationship between these measures and hearing aid benefit?

Expected Outcomes

- a. This population of veterans will differ from veterans with no history of blast exposure, and the presence of PTSD will increase severity and alter the deficit pattern.
- b. This population of veterans will experience significant problems with the addition of background noise and the effect will be influenced by linguistic load, verbal working memory and attention.
- c. This population of veterans will demonstrate and perceive benefit from being fitted with mild-gain high-frequency hearing aids, although the coexistence of PTSD will restrict perceived benefit.
- d. Mild-gain high-frequency amplification will improve speech perception skills in quiet and noise, and improve linguistic processing and executive function.
- e. Benefit from amplification will relate to the deficits that the veterans present.

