Delayed-Treatment Control Group – The participants in the delayed-treatment control group will be selected from the mTBI-only group and followed over a 12-month period (+/- 2 weeks). At the onset of Part 2 they will complete the HHIA, SSQ, and the unaided portion of the APHAB. They will complete the speech perception and language tasks administered to the treatment group (CCT, phonetic context effect, and CRTT tasks) but unaided only. The delayed-treatment groups will receive home visits at 1, 2, 4 months (+/- 1 week) post-entry, at which times they will complete the HHIA, SSQ, and the unaided portion of the APHAB. At 6 months post-entry their pure tone hearing thresholds will be measured to determine possible changes in hearing sensitivity, and the procedures used with the treatment groups will be applied with the same sequence of follow-up sessions.

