and investigators, when possible, will participate in public events for veterans (e.g., Research Week, VA athletic events and fairs, Veteran's information tables at local university information and health fairs) where flyers and information will be offered about the study. Potential veterans can provide contact information at the time of the events if interested in participating in the study, or they can contact the study personnel at a later time. At the onset of the study and during Years 3 and 4, a review of audiology records in CPRS may be conducted for each site to identify possible participants based on target age range and normal or near normal pure tone audiometric test results. These individuals will be sent a letter describing the study and inviting them to contact local study personnel if they are interested in participating in the study. Also included in the mailing will be a stamped return envelope and a form that the veterans can return indicating that they would like to be contacted via telephone to discuss the study or opt-out and not be contacted about the study. Veterans who fail to return the form within 2 weeks will be contacted by telephone by study staff members to determine if they received the mailing. After the letters have been mailed, all information obtained from CPRS will be maintained in accordance with the VHA Records Control Schedule. Social Security Numbers will be used for CPRS access for recruitment, and then later for study data collection and subject payment purposed.

The significant others completing the HHIA-SO will be a family member or friend selected by the veteran participating in the study. The significant other is not required to complete or mail the questionnaire, and the veteran will not be penalized or withdrawn from the study if the questionnaire is not returned or if they do not have a person available or willing to complete the questionnaire.

Part 2

A subset of the participants from the mTBI-only and mTBI+PTSD groups from Part 1 will be selected to participate in Part 2. They will be placed into four groups of 25. The groups will consist of an mTBI-only treatment group and an mTBI+PTSD treatment group, along with an mTBI-only delayed-treatment control group and an mTBI+PTSD delayed-treatment control group.

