Using the order in which participants complete Part 2 as an identifier, the participants from the mTBI-only and mTBI+PTSD groups will be randomly assigned to receive either treatment or delayed treatment, and then ranked in random order for participation in Part 2. Each of the groups will be populated using this selection procedure. The assignments will be determined at the onset of the study by the PI with subsequent replacement as needed. Because Part 2 is preliminary in nature (not a randomized control trial) and includes low numbers of participants, any participants opting out of Part 2 will be replaced using the rank ordered list. Participants will be informed at the conclusion of Part 1 whether they can enroll in Part 2. If participants do not qualify, they will be informed that they could be contacted at a later date to act as a replacement. The study staff will be responsible for discussing enrollment in Part 2 with participants.

Payment

The veteran participants will be paid \$50 per session (laboratory and home visits) for their participation, and a \$25 travel allowance for each session requiring travel to one of the testing sites. They will be paid through the preferred method at each site (e.g., Financial Management System, vouchers, payment cards). When the Financial Management System is used the payment will not be immediate. The significant others who complete the HHIA-SO will not receive any payment.

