Sample Size and Power – This analysis will include data from 100 participants (25 for each group). For any comparisons of the four groups based on ANOVA with a significance level of 0.01 to account for multiple comparisons and a power of 0.80, an effect size of 0.38 or greater will be detectable. For the paired analyses described above, there is sufficient power (0.80) to detect an effect size of 0.50 (baseline versus 6 months) or 0.50 (baseline versus 12 months), or greater assuming a two-sided significance level of 0.01 to account for multiple comparisons. For the longitudinal modeling, there will be sufficient sample size to support the proposed modeling that will allow approximately 10 observations to be estimated for each parameter. The number of covariates in each model will depend on the sample size to insure that there are approximately 10 observations available for each parameter estimated. For correlation

based analyses, the study is powered (0.80) to detect correlations of 0.26 or greater in absolute value for a total sample size of 100.

Once the data are formatted and cleaned by a staff member at the VA Pittsburgh site under the supervision of the statistician, the data will be analyzed by the statistician.

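### Section 5.1 draws the Part 2 delayed-treatment control from mTBI-only alone, while 5.2 and 5.6 have one in each PTSD stratum; followed literally, 5.1 would remove the controlled treatment-by-PTSD contrast

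*Combined protocol and SAP*

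**What the plan says.** Section 5.1, in the paragraph on the delayed-treatment control, gives the source of the controls: "The participants in the delayed-treatment control group will be selected from the mTBI-only group and followed over a 12-month period". Later in the same paragraph the wording turns plural: "The delayed-treatment groups will receive home visits at 1, 2, 4 months".

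Section 5.2 (Part 2) describes a different layout: "They will be placed into four groups of 25". It lists a treatment group in each stratum, "along with an mTBI-only delayed-treatment control group and an mTBI+PTSD delayed-treatment control group". On allocation it says that "the participants from the mTBI-only and mTBI+PTSD groups will be randomly assigned to receive either treatment or delayed treatment".

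Section 5.6 (Part 2 Analysis) refers to delayed-treatment groups in the plural. Its power paragraph says "This analysis will include data from 100 participants (25 for each group", and its ANOVA statement begins "For any comparisons of the four groups based on ANOVA with a significance level of 0.01 to account for multiple comparisons".

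The research question at stake is question d in section 3.0. It asks whether these veterans benefit from mild high-frequency gain and "does PTSD influence benefit".

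**The concern.** The two layouts cannot both be followed. One has a single delayed group from mTBI-only; the other has a delayed group in each PTSD stratum.

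A controlled answer to the PTSD part of question d is a difference of differences: treated minus delayed change in mTBI+PTSD, less the same quantity in mTBI-only. The HHIA, SSQ and APHAB are self-reported and given repeatedly, and the CCT and CRTT are re-administered, so retest and time effects are plausible. The delayed groups' untreated first six months are the plan's means of estimating those effects between visits. Without a delayed mTBI+PTSD group, change over time in that stratum cannot be separated from the effect of the aids, unless untreated change is assumed equal in the two strata. A control group omitted during conduct cannot be recovered at analysis.

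**Working it through.** **Which text is the outlier.** Four places support a delayed group in each stratum: the list of groups in 5.2, the allocation rule in 5.2, the plural in the 5.6 analysis text, and the four groups of 25 in the 5.6 power text. One sentence in 5.1 supports mTBI-only alone, and its own paragraph later uses the plural.

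**Inputs.** From 5.6: four groups, N = 100, 25 per group, alpha 0.01, power 0.80, stated ANOVA effect 0.38, stated paired effect 0.50 at 6 and at 12 months (two-sided 0.01). Assumed for the literal 5.1 reading: three groups of 25, N = 75.

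**ANOVA.** Noncentral F with k − 1 and N − k degrees of freedom and noncentrality λ = f²N.

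- Plan's own case, k = 4, N = 100: critical F(3, 96) = 3.99. At f = 0.38, λ = 0.1444 × 100 = 14.44 and power is 0.73. Power 0.80 needs f = 0.405, so 0.38 is not reproduced. Detecting 0.38 with four groups takes 29 per group (116 in all).
- Three groups sharing N = 100 give f = 0.382, close to the stated figure.
- Literal 5.1 reading, k = 3, N = 75: critical F(2, 72) = 4.91. At f = 0.38, λ = 0.1444 × 75 = 10.83 and power is 0.62. Power 0.80 needs f = 0.444.

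The like-for-like loss from dropping the group is therefore 0.405 to 0.444, or 0.039. The remaining 0.405 − 0.38 = 0.025 is a separate discrepancy in the stated figure.

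**Paired test.** Noncentral t with n − 1 degrees of freedom and noncentrality d√n, two-sided 0.01.

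| n | Detectable d (power 0.80) | Power at d = 0.50 |
|---|---|---|
| 25 | 0.735 | 0.40 |
| 50 | 0.500 | 0.80 |
| 100 | 0.348 | 0.99 |

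The stated 0.50 is reproduced at n = 50. For the 12-month comparison, that means both delayed groups of 25 pooled; a single delayed group of 25 does not support it.

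**Estimability.** Take the model with intercept, treatment, PTSD and treatment × PTSD. With all four cells the design matrix has rank 4 for four parameters. Without the delayed mTBI+PTSD cell it has rank 3, so the interaction is not estimable.

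**Precision with four groups of 25.** In SD units of the analysed outcome or change score:

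- Treated versus delayed in one stratum: SE = √(2/25) = 0.283, df = 48. Detectable difference 0.81 SD (alpha 0.05) or 1.00 SD (alpha 0.01).
- Treatment × PTSD interaction: SE = √(4/25) = 0.40, df = 96. Detectable difference 1.13 SD (alpha 0.05) or 1.39 SD (alpha 0.01).

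**Timing.** The paired test in 5.6 takes the treated groups from baseline to 6 months and the delayed groups from baseline to 12 months. Under 5.1 the delayed participants enter the treatment procedures at 6 months, so their 12-month score is post-fitting. That test makes no treated-versus-untreated comparison under either layout; the untreated window is months 0 to 6.

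**The case against.** The strongest reply is that this is one stray sentence. Its own paragraph later uses the plural, 5.2 and 5.6 agree with each other, and 5.2 has the PI fix the assignments at the start of the study from both strata. Sites therefore do not build the groups from the 5.1 paragraph, which mainly sets out the delayed visit schedule. This stands: the harm is conditional, and the documents do not show that only three groups, or 75 people, would be enrolled.

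A reader might also infer that question d could not be answered at all under the 5.1 wording. The documents do not support that. Change in the two treated groups could still be compared by PTSD status (25 versus 25, detectable at 1.00 SD at alpha 0.01). Section 5.1 also has the CCT, CRTT, CRTT-R and phonetic context tasks done with and without aids at the 1-week and 6-month laboratory sessions. Those same-visit differences are much less exposed to drift between visits. What would be lost is the controlled contrast.

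Nor do all the Part 2 power figures rest on 100 people in four groups: the paired figure matches n = 50 and the ANOVA figure matches three groups sharing 100. It is tempting to read the latter as a relic of a three-group design, but the documents do not say so.

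Finally, 5.2 calls Part 2 preliminary and not a randomized controlled trial. That excuses limited power. It does not excuse doubt about which control groups exist.

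**Conclusion.** The contradiction is certain and lies in the current text. Section 5.1 gives a selection rule that conflicts with 5.2 and 5.6 and would, if applied, remove the untreated mTBI+PTSD comparator. The consequence depends on 5.1 being followed and, for the numbers, on 25 per group. On that reading the controlled treatment-by-PTSD contrast is not estimable, the detectable f rises from 0.405 to 0.444, and the 12-month paired test has power 0.40 at the stated 0.50.

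Correcting the sentence is necessary but does not by itself give a treated-versus-untreated test, because the primary paired analysis reads the delayed groups after fitting. Even with all four groups, only interactions of about 1.1 to 1.4 SD are detectable, so an answer on PTSD and benefit will be exploratory. The failure of 0.38 to reproduce for four groups is a separate, smaller discrepancy.

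**What to change.** 1. Amend the delayed-treatment paragraph in 5.1 so that delayed controls are randomised from both mTBI-only and mTBI+PTSD, 25 each, and use the plural throughout, in line with 5.2 and 5.6.
2. In 5.6, name the analysis for the PTSD part of question d: treated-minus-delayed change over months 0 to 6, by PTSD stratum, and the difference between strata. The group-by-time mixed model already planned can supply it as a contrast. Confirm in 5.1 that the delayed groups complete the outcome measures at 6 months before fitting.
3. Label this interaction exploratory and report its detectable size (about 1.1 SD at alpha 0.05, 1.4 SD at alpha 0.01).
4. In the power paragraph, replace 0.38 with 0.405 for four groups of 25 or explain its basis, and say that the paired 0.50 assumes 50 people, with both strata pooled.

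The cost is a short text amendment and one prespecified contrast. The stated total of 100 is unchanged.

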5.2 Recruitment Methods

Part 1 Recruitment

The participants (other than significant others) completing this study will be veterans aged 20 to 50 years and divided into 4 groups: 2 groups of 117 veterans who report histories of blast exposure and blast-related clinical signs consistent with the VA/DoD definition of mTBI (VA/DoD, 2009) and present with normal or near normal results on standard audiometric testing but who report substantive problems with audition; a group of 117 normal hearing controls who report no auditory problems and no histories of blast exposure, brain injury or psychiatric disorder (Normal Controls); and a group of 117 normal hearing veterans with PTSD and no blast exposure or blast-related clinical signs (PTSD-only). Of the two groups of veterans with auditory complaints one group will present with little or no PTSD (mTBI-only), whereas the other group will be symptomatic for PTSD (mTBI+PTSD). A total of 468 participants will complete the study and 50 additional participants will be allowed for experimental attrition. It should be noted that the participants do not need to have a previous diagnosis of mTBI or PTSD, or even believe that they have mTBI or PTSD to participate in this study.

All these participants (including normal controls) will be recruited using the following procedures. They will be recruited through flyers distributed in various clinics (e.g., audiology, behavioral health, neuropsychology) at the three participating VA sites. In addition, participants will be recruited through research registries at the study sites and national VA and military research registries, such as the Corporate Data Warehouse through Data Access Request Tracker (DART) via the VA Data Portal/VINCI and the VA database for individuals who have initial positive TBI screens (<https://vssc.med.va.gov/tbireports/TBI.aspx>). The study will adhere to contact methods approved by the individual registries. Flyers and list serve announcements will be provided to veteran organizations/offices at the university affiliates of the participating sites for distribution (flyer and announcement attached). Flyers and list serve announcements also will be provided to local veteran organizations for distribution. Clinical audiologists at the three sites will be informed of the study and if they so choose, can provide potential participants with flyers so that the potential participants can contact study personnel to learn more about the study. Research staff members

and investigators, when possible, will participate in public events for veterans (e.g., Research Week, VA athletic events and fairs, Veteran's information tables at local university information and health fairs) where flyers and information will be offered about the study. Potential veterans can provide contact information at the time of the events if interested in participating in the study, or they can contact the study personnel at a later time. At the onset of the study and during Years 3 and 4, a review of audiology records in CPRS may be conducted for each site to identify possible participants based on target age range and normal or near normal pure tone audiometric test results. These individuals will be sent a letter describing the study and inviting them to contact local study personnel if they are interested in participating in the study. Also included in the mailing will be a stamped return envelope and a form that the veterans can return indicating that they would like to be contacted via telephone to discuss the study or opt-out and not be contacted about the study. Veterans who fail to return the form within 2 weeks will be contacted by telephone by study staff members to determine if they received the mailing. After the letters have been mailed, all information obtained from CPRS will be maintained in accordance with the VHA Records Control Schedule. Social Security Numbers will be used for CPRS access for recruitment, and then later for study data collection and subject payment purposed.

The significant others completing the HHIA-SO will be a family member or friend selected by the veteran participating in the study. The significant other is not required to complete or mail the questionnaire, and the veteran will not be penalized or withdrawn from the study if the questionnaire is not returned or if they do not have a person available or willing to complete the questionnaire.

Part 2

A subset of the participants from the mTBI-only and mTBI+PTSD groups from Part 1 will be selected to participate in Part 2. They will be placed into four groups of 25. The groups will consist of an mTBI-only treatment group and an mTBI+PTSD treatment group, along with an mTBI-only delayed-treatment control group and an mTBI+PTSD delayed-treatment control group.

Using the order in which participants complete Part 2 as an identifier, the participants from the mTBI-only and mTBI+PTSD groups will be randomly assigned to receive either treatment or delayed treatment, and then ranked in random order for participation in Part 2. Each of the groups will be populated using this selection procedure. The assignments will be determined at the onset of the study by the PI with subsequent replacement as needed. Because Part 2 is preliminary in nature (not a randomized control trial) and includes low numbers of participants, any participants opting out of Part 2 will be replaced using the rank ordered list. Participants will be informed at the conclusion of Part 1 whether they can enroll in Part 2. If participants do not qualify, they will be informed that they could be contacted at a later date to act as a replacement. The study staff will be responsible for discussing enrollment in Part 2 with participants.

Payment

The veteran participants will be paid \$50 per session (laboratory and home visits) for their participation, and a \$25 travel allowance for each session requiring travel to one of the testing sites. They will be paid through the preferred method at each site (e.g., Financial Management System, vouchers, payment cards). When the Financial Management System is used the payment will not be immediate. The significant others who complete the HHIA-SO will not receive any payment.

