- d. Staggered Spondaic Word Test (SSW) to measure timing and inter-hemispheric processing of words
- e. Gaps in Noise Test (GIN) to assess temporal processing in noise
- f. Auditory brainstem response (ABR), middle latency response (MLR), long-latency response (LLR) and active event-related P300 to assess the electrophysiological status of the central auditory system.

Speech and Language Processing in Noise –

- a. The Words-in-Noise test (WIN; VA Compact Disk 4.0; Wilson & Burk, 2005) to target listening at the single word level
- b. The Listening in Spatialized Noise - Sentences Test (LiSN-S; Cameron & Dillion, 2012) to assess sentence perception in noise within a simulated 3-dimensional acoustic space
- c. Auditory and reading versions of subtests 1 through 10 from the Computerized Revised Token Test (CRTT and CRTT-R respectively; McNeil et al., 2009) will be administered in quiet and in +3 dB signal-to-babble to assess sentence level processing in both auditory and reading domains. The preliminary CRTT pretests will be administered prior to these tests to assure that the participants have the basic skills to complete the tasks and to measure baseline reaction time.

Executive Function –

- a. Digit span forwards and backwards both acoustically and visually according to Kemtes and Allen (2008) to assess verbal short term and computational memory skills
- b. The CRTT Stroop task (CRTT-R-Stroop; McNeil et al., 2010) to assess the interaction between language and executive function
- c. Rey Auditory Verbal Learning Test (Schmidt, 1996) to assess immediate and delayed verbal memory, efficiency of learning and the effects of interference
- d. Trail Making Test (Reitan, 1992) to measure attention and processing speed

PART 2 Procedures

Hearing Aid Fittings (treatment groups) – In Part 2 a subset of the participants from the mTBI-only and mTBI+PTSD groups from Part 1 will be fitted binaurally with open-fit hearing aids with mild high-frequency gain. Each group will consist of 25 participants. They will be randomly selected and randomly replaced if they decline to participate at any point during the treatment protocol.

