5.3 Informed Consent Procedures

The veteran participants will complete a telephone screen to ensure that they meet basic criteria and to reduce burden for those veterans who would not qualify from the onset. The study will be described to them and if they remain interested in participation verbal permission will be requested to ask the screening questions (See script and flow chart for telephone screen.)

Written and verbal informed consent will be obtained from the veteran participants before implementation of the remaining study procedures. Two consent forms; one for each part of the study and will be completed. The consent form for Part 1 will be completed by all participants and the consent form for Part 2 will only be signed by participants who complete Part 1 and are selected to complete Part 2. Informed consent will be obtained from the participants in person in a private room by the investigators or study staff approved to obtain informed consent. Human subjects protection requirements and how to obtain and document informed consent will be reviewed during the initial training of study personnel to insure procedural uniformity across sites. The training will occur at the beginning of the study and as new personnel are added to the study by the lead investigators at each site.

Written and verbal informed consent will not be obtained from the significant others who complete the HHIA-SO. The instructions will indicate that completion and mailing of the questionnaire will be voluntary and that all information on the questionnaire will be kept confidential and not accessible to the veteran. No identifying information will be requested or included on the questionnaire except for the subject ID number assigned to the veteran participant.

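### Part 2 arms are set in advance by the PI with no concealment described and decliners replaced, so arm-dependent entry or opt-out could affect the between-group comparisons

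*Combined protocol and SAP*

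**What the plan says.** Section 5.2 (Part 2) plans four groups of 25: treatment and delayed treatment within each of the mTBI-only and mTBI+PTSD groups. Participants "will be randomly assigned to receive either treatment or delayed treatment, and then ranked in random order for participation in Part 2". The key linking a person to an assignment is given as "Using the order in which participants complete Part 2 as an identifier". On who sets the list and when: "The assignments will be determined at the onset of the study by the PI with subsequent replacement as needed". On opt-outs: "any participants opting out of Part 2 will be replaced using the rank ordered list". On the approach to participants: "The study staff will be responsible for discussing enrollment in Part 2 with participants".

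Section 5.1 (Part 2 Procedures) adds that members of the treatment groups are "randomly replaced if they decline to participate at any point during the treatment protocol".

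Section 5.3 says the Part 2 consent form "will only be signed by participants who complete Part 1 and are selected to complete Part 2", and that consent is obtained "by the investigators or study staff approved to obtain informed consent".

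Section 5.2 also describes Part 2 as preliminary and not a randomized controlled trial. The available text names no independent list holder, no sealed or central release, no restriction on who may see the list, and no rule that the arm is revealed only after consent and baseline.

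**The concern.** A random sequence protects a comparison only if people enter it without regard to the arm that comes next. Here the sequence exists from the start, it is known to an investigator, and consent is sought afterwards.

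The two offers also differ. One group is fitted at once and followed for 6 months. The other waits 6 months for its aids and is followed for 12. Willingness to join or stay could differ by arm even if every member of staff behaves perfectly. Because those who leave are replaced, the 25 people analysed in a group need not be the 25 first assigned to it.

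At stake is the reading of the delayed-treatment groups as controls. A paired change from baseline cannot tell a hearing-aid effect from retest or time effects. The planned analyses that can do so are those comparing groups, and they need comparable arms.

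**Working it through.** The plan states no figure on this point, so the check sets the provisions side by side and then gives an illustration.

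**Order of events**

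1. Arms are determined at study onset by the PI (5.2).
2. The participant completes Part 1, usually in 4 to 5 sessions with 4 more allowed (5.1).
3. The participant is told whether Part 2 is open to them (5.2). Selection and arm come from the same procedure.
4. Part 2 consent is signed by those already selected (5.3), and investigators are among those who may obtain it.
5. Pretreatment measures are taken (5.1).
6. Opt-outs are replaced from the ranked list (5.2). For the treatment groups, replacement may occur at any point in the treatment protocol (5.1).

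Step 1 precedes steps 4 and 5, so the arm is fixed, and known to at least the PI, before consent and baseline. Step 6 allows substitution after the arm is known. The open routes are foreknowledge of the list, the timing of completion if completion order is the key, the way enrolment is discussed, and arm-dependent opt-out followed by replacement.

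**The identifier**

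The order of completing Part 2 is not known until Part 2 is over, yet it is meant to index assignment into Part 2. The rule cannot be followed as written. Order of completing Part 1 was presumably meant; that is an assumption.

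**Which analyses are exposed (5.6, Part 2)**

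| Analysis | Relies on comparable arms? |
|---|---|
| Paired t or signed rank test on behavioural measures, within group | No |
| ANOVA or Kruskal-Wallis on questionnaire scores between the mTBI groups | Yes |
| Mixed model with group, time and group-by-time (secondary) | Yes, for differences in change |

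In the mixed model, a difference in baseline level alone does not bias the interaction. The people gained or lost would have to change differently over time.

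**Illustration of size**

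The documents give no value for a shift between arms, so b below is assumed. Take a two-sample t test at two-sided 0.05 with n per arm, no true effect, and a shift of b SD in the outcome compared. The noncentrality is b × √(n/2) with 2n − 2 degrees of freedom. For b = 0.2 this is 0.2 × √12.5 = 0.71 at n = 25, and 0.2 × √25 = 1.00 at n = 50.

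| Assumed b (SD) | False-positive rate, 25 v 25 (one PTSD stratum) | False-positive rate, 50 v 50 (strata pooled) |
|---|---|---|
| 0 | 5% | 5% |
| 0.1 | 6.4% | 7.9% |
| 0.2 | 10.7% | 16.8% |
| 0.3 | 18.0% | 31.8% |
| 0.5 | 41.0% | 69.7% |

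One way to reach the low end of this range: if 10% to 30% of entries depended on arm, all in one direction, and those people differed by 0.5 SD, then b = 0.10 × 0.5 = 0.05 to 0.30 × 0.5 = 0.15. Both inputs are assumptions.

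**The case against.** The strongest reply is that the text is silent on concealment, and silence is not evidence that it is absent. A reader might infer that recruiting staff know the next arm and can steer people. The documents do not say that staff see the list or that the arm is disclosed before consent; participants are told whether they can enrol, which is not the same as being told the arm. Section 8.0 expects half of accrual at the two sites other than Pittsburgh, so the PI's knowledge does not show that recruiters there share it. The text of Sections 1.0 and 4.0, on personnel, was not available for this check. This objection stands. What can be said is that no concealment is described and that the PI has foreknowledge.

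Second, assignment and ranking are random and replacements follow the ranking. This also stands: the PI is not described as choosing arms at discretion, and the random order limits steering. It does not remove it, because random and concealed are different properties, and nobody can randomise who opts out.

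Third, Part 2 is declared preliminary, and its main test of change is within group on behavioural measures. That narrows the harm. But the same section assigns at random and names control groups, and the questionnaire ANOVA is listed among the primary analyses, so the between-group comparison is meant to be used.

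Fourth, a reader might infer that the bias would go unseen because outcomes are self-reported and testers unblinded. The documents do not support this. Behavioural tests and data-logged use time are collected alongside the questionnaires, and tester masking is simply not addressed. Everyone eligible for Part 2 has completed the Part 1 battery, so imbalance on measured traits can be examined, including between those who enter and those who decline. Only unmeasured differences would stay hidden.

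**Conclusion.** The point holds in a limited form. As written, the Part 2 arms are determined before consent by the PI, no concealment is described, and people who decline or leave are replaced, so arm-dependent consent or opt-out can alter the make-up of each arm. The exposure is confined to the questionnaire ANOVA and the group-by-time model.

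Its size cannot be estimated. The illustration suggests a modest effect for small shifts (6.4% to 16.8% false positives for 0.1 to 0.2 SD, depending on pooling) and a serious one only for shifts that nothing in the documents establishes. It also assumes a simple two-group test at an unadjusted 0.05, not the planned analyses after false discovery rate adjustment.

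The identifier is a plain error that must be corrected whatever view is taken of concealment. The change is worth making before further Part 2 enrolment, but the point does not invalidate Part 2.

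**What to change.** - Replace the identifier with one that exists at assignment. If Part 1 completion order was meant, say so.
- Keep the random rank order for choosing who is invited to Part 2, but separate it from the arm.
- Have the study statistician generate and hold the treatment/delayed list, stratified by PTSD group, and release each arm only after Part 2 consent is signed and the pretreatment measures are complete.
- State who may see the list.
- Log everyone invited who declines. With release after consent, these people have no arm yet, and their Part 1 data allow comparison with those who enter.
- Report dropouts after assignment by assigned arm, and report replacements separately.

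The stratified list assumes delayed-treatment groups in both PTSD strata, as Section 5.2 has it. Section 5.1 draws the delayed group from mTBI-only, and the two must be reconciled first.

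The cost is protocol wording and some of the time of a statistician already on the study. The small downside is that assignments must be released one at a time across three sites.
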